2. **Increase the continuation of highly effective contraceptive use at 3, 6, and 9 months.** Hypothesis: Girls randomized to CAMI will be more likely to continue the use of highly effective contraception at 3, 6, and 9 months after CAMI intervention compared to girls randomized to DEC. The **primary outcome** is continued highly effective contraceptive use at 3, 6, and 9 months. This will be measured through calendar-assisted self-report. The **secondary outcome** is pregnancy as documented by a urine pregnancy test at each follow-up visit.
3. **Decrease unsafe sexual activity.** Hypothesis: CAMI will decrease unsafe sexual behavior more than DEC. The **primary outcome** is an incident STI after a negative baseline test. The **secondary outcome** is intercourse that is poorly protected against STIs at 3, 6, and 9 months as determined by calendar-assisted self-report.

Study Design and Methods

Recruitment.

Participants were recruited from the RI Juvenile Probation Department (JPD), RI group homes and alternative schools, Job Corps of Rhode Island and Community Mental Health Centers. Girls between the ages of 14 to 21 at each of these sites were approached for recruitment. Girls who were interested in participating were provided further detail, and inclusion and exclusion criteria were reviewed. When eligible and willing to participate in the study, the informed consent process was completed (study explained, consent form read to the individual, questions answered) and forms signed. Locator information was obtained, and consents signed for tracking.

Assessment and Randomization.

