Sample size was determined using power analysis for hypothesis tests related to primary aims. Based on the power analysis, a total of 250 teens were to be recruited in order to retain a minimum sample size of about 200 (80% retention) at 9-mo follow-up (FU). Anticipated FU rates were 90%, 85% and 80% at 3-, 6- and 9-mo FU, respectively. These numbers are conservative and are based on comparable recruitment and FU rates as found in the principal investigator’s lab. In probation alone, about 311 female teens per year were placed on probation and about 85% met screening criteria (see above). See Table 1 for the study’s anticipated flow. Youth were recruited from venues on a first come.

Participant Flow:

Year	Baseline	3 Month Follow-Up	6 Month Follow-Up	9 Month Follow-up
1	47	28	10	0
2	72	64	60	48
3	72	63	60	53
4	59	62	60	54
5	0	8	22	45
Total	250	225	212	200

Primary Outcomes (assessed at baseline and follow-ups).

Initiation and Continuous Use of Highly Effective Contraceptives at 3, 6, and 9 Months. A participant switching from one highly effective contraceptive method to another was recorded as maintaining continuous contraceptive use at follow-up if she switched methods during times when the original method was still effective. Use of contraceptive methods was assessed through the TLFB (see below).

Incident STIs. At baseline participants were tested for *T. vaginalis*, *N. gonorrhoeae*, and *C. trachomatis* through self-obtained vaginal swabs. If a participant was diagnosed with an STI at baseline she was to be referred for treatment at a Title X clinic and retested at her next follow-up visit. Any positive test after a baseline negative test was documented as an incident infection. These STIs encompass the most common infections seen in sexually active girls and can result in adverse reproductive sequelae such as infertility, chronic pelvic pain, increased HIV risk and elevated risk of ectopic pregnancy. Other STIs (human papilloma virus, Herpes simplex virus and Syphilis) are not included as the incidence of primary disease in RI is low and diagnosis may require a physical exam or serology.

Secondary Outcomes (assessed at baseline and follow-ups).

Incident Pregnancy. An incident pregnancy was defined as having occurred if there is a baseline negative pregnancy test and a positive urine at follow-up (using a Beta-HCG test) or a self-reported pregnancy confirmed with a positive urine.

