Satisfaction Survey. CAMI and DEC participants completed this 18-item survey of closed and open-ended questions on acceptability of the computerized assessment and counseling. The CAMI participants' survey also contains questions about the perceived fit of the risk assessments for pregnancy and STIs and acceptability of the SAFE plan. All participants completed an abbreviated satisfaction survey at the 9-month follow-up to assess long term satisfaction with the intervention.

Data Analysis.

Sample Size Considerations. Based on the following calculation, we proposed baseline N = 250 subjects.

Specific Aim #1, increasing initiation of highly effective contraception. It is anticipated that CAMI intervention to have a moderate effect on contraceptive initiation rate, resulting in 20% starting a contraceptive method in the treatment group. **Follow-up N = 200 will provide 95% power with a 0.05 two-sided significance level.**

Specific Aim #2, continuation of highly effective contraceptives. Assuming an average within-subject correlation of 0.50, corresponding to a design effect of 2.5, approximately 125 subjects for each group at baseline will provide 80% power for this analysis. In other words, the proposed total sample size of 250 participants at baseline will be enough to achieve excellent

power after considering 20% attrition rate over 9 months (assume continuation increase of 9% for controls and 24% for the intervention group, based on CAMI pilot data).

The secondary outcome of documented pregnancy (Aim 2) will not be powered to detect between group differences. These data are exploratory in nature and inexpensive.

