Missing Data. Because the primary outcome variable, initiation of a contraceptive method, was to be observed for all participants, missing data posed minimal threat to the internal validity of the intervention in determining contraceptive initiation. In the event of item non-response occurring, multiple imputation was to be used to estimate adjusted treatment effects.²⁴ For multiple imputation, 10 data sets were to be generated using SAS Proc MI and the companion procedure PROC MIANALYZE was to estimate the logistic regression model corresponding to analyses for each of the individual aims. If there were differences in the outcomes as a function of missing data pattern, then missing data pattern was to be included as covariate in the analyses.

Literature Cited

1. Guttmacher (2019). Unintended pregnancy in the US. *Fact Sheet*, Guttmacher Institute, NY. Accessed 2-17-23, www.guttmacher.org/fact-sheet/unintended-pregnancy-united-states.
2. Centers for Disease Control (CDC). (2020). Youth risk behavior survey, data summary & Trends report. *National Center for HIV, Viral Hepatitis, STD & TB Prevention, Div of Adolescent & School Health*. Accessed 2-17-23, www.cdc.gov/healthyyouth/data/yrbs/pdf/yrbs_data-summary-trends_report2023_508.pdf
3. DiClemente, R. J., Davis, T. L., Swartzendruber, A., Fasula, A., Boyce, L., Gelaude, D., ...Staples- Horne, M. (2014). Efficacy of HIV/ STI risk reduction intervention for African American adolescent girls in juvenile detention centers. *Women & Health*, 54(8), 726-749. <https://doi.org/10.1080/03630242.2014.932893>
4. Coyle K. K., Franks H. M., Glassman, J. R., & Stanoff, N. M. (2012). Condom use: Slippage, breakage, and steps for proper use among adolescents in alternative school settings. *Journal of School Health*, 82(8), 345-352. <https://doi.org/10.1111/j.1746-1561.2012.00708.x>
5. Brown, L. K., Hadley, W., Stewart, A., Lescano, C., Whiteley, L., Donenberg, G., & DiClemente, R. (2010). Psychiatric disorders & sexual risk among adolescents in mental health treatment. *Journal of Consulting and Clinical Psychology*, 78(4), 590-597. <https://doi.org/10.1037/a0019632>

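### Do the unstated rates behind the powers for Aims 1 to 3 call the planned 250 girls into question?

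*Combined protocol and SAP*

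**What the plan says.** The Sample size section sets recruitment at 250 so that about 200 remain at 9 months, with expected retention of 90%, 85% and 80% at the three visits. The power claims are in Data Analysis, Sample Size Considerations.

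- **Aim 1 (initiation).** A moderate effect is expected, "resulting in 20% starting a contraceptive method in the treatment group", and "Follow-up N = 200 will provide 95% power with a 0.05 two-sided significance level". No DEC rate is given. The Missing Data section adds that the primary outcome, "initiation of a contraceptive method, was to be observed for all participants".
- **Aim 2 (continuation).** The clustering input is given as "Assuming an average within-subject correlation of 0.50, corresponding to a design effect of 2.5". The power claim that rests on it is that "approximately 125 subjects for each group at baseline will provide 80% power for this analysis". The rates appear in a parenthesis: "assume continuation increase of 9% for controls and 24% for the intervention group, based on CAMI pilot data". Study Objectives defines the outcome as "continued highly effective contraceptive use at 3, 6, and 9 months".
- **Aim 3 (unsafe sex).** With correlation 0.50 and 20% attrition, 80% power is claimed for incident STI over three repeated measures (3, 6 and 9 months), and 97% for the secondary outcome. No STI rate, unsafe-sex rate or difference is stated for either.

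**The concern.** A power figure can be checked only if the rate in each arm, the number analysed and the contrast tested are all known. Aim 1 lacks the control rate and Aim 3 lacks both rates. Aim 2 has rates, but calls them increases without giving a starting level. Its design effect of 2.5 at correlation 0.50 implies four occasions, while the outcome is defined at three. The Aim 2 analysis paragraph describes a treatment-by-time test and does not say whether the 80% refers to it.

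These claims are the stated basis for 250 girls, and the missing inputs matter: a few points on the Aim 1 control rate separate strong power from modest power. If the true planning rates were unfavourable, a null result could reflect a small trial rather than an ineffective intervention, and a reader could not tell which.

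**Working it through.** **Method.** Two-sided alpha 0.05, n per arm, rates p1 and p2, difference d, mean rate p. Power = Φ((d − 1.96·se0)/se1), with se0 = √(2p(1−p)/n) and se1 = √((p1(1−p1)+p2(1−p2))/n). For repeated visits, effective n = n·m/DE, where DE = 1 + (m−1)·0.50 for m occasions. The base is n = 100, from 200 retained and equal arms.

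**Aim 1.** CAMI 20% is stated; every DEC rate below is an assumption. At DEC 4%: d = 0.16, se0 = 0.0460, se1 = 0.0445, so Φ(1.57) = 94.2%.

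| Assumed DEC rate | Power, 100 per arm | Power, 125 per arm |
|---|---|---|
| 3% | 97.0% | 99.0% |
| 4% | 94.2% | 97.7% |
| 5% | 90.0% | 95.2% |
| 7% | 77.1% | 85.7% |
| 9% | 60.0% | 69.7% |

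Exactly 95% at 100 per arm needs a DEC rate of about 3.75%. Two other readings land close to the stated figure. Taking moderate as Cohen's h = 0.5 gives Φ(0.5·√50 − 1.96) = Φ(1.58) = 94.2%, with a DEC rate of 4.5%. Taking the 20% as a 20-point rise over 9% or 10% gives 95.6% or 94.8%. So 95% is attainable on several readings, and the text does not say which was meant.

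**Aim 2.** First, 9% and 24% as final proportions at one visit: d = 0.15, se0 = 0.0525, se1 = 0.0514, so Φ(0.917) = 82.0%. Fisher's exact test gives 78.5% and a log-odds Wald test 78.8%. The n for 80% is 95 per arm, or 95/0.8 = 119 at baseline; with continuity correction it is 108, or 108/0.8 = 135. The stated 125 lies between these, so 80% with 125 per arm is approximately recovered as a single-visit comparison.

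Next, the design effect. Three visits give 1 + 2(0.50) = 2.0; the stated 2.5 equals 1 + 3(0.50), which is four occasions. The fourth could be baseline, where the Primary Outcomes section says these outcomes were also assessed. Baseline precedes counselling and cannot carry a treatment difference, so no power is computed on that footing. With three visits:

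- DE 2.0: effective n = 100·3/2.0 = 150, power 94.2%.
- DE 2.5: effective n = 100·3/2.5 = 120, power 88.4%.

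On this reading the larger design effect is the more cautious one, and both results exceed 80%. Dividing 100 by 2.5 would give 43.8%, but that charges the penalty for repeated observations without counting the observations.

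If 9% and 24% are increases over an assumed starting level of 10%, 20% or 30%:

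| Reading | 10% | 20% | 30% |
|---|---|---|---|
| One visit | 67% | 60% | 57% |
| Three visits, DE 2.5 | 75% | 68% | 65% |
| Three visits, DE 2.0 | 84% | 77% | 74% |

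These fall on both sides of 80%, and each uses a starting level that the documents do not give.

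**Aim 3.** Three visits are stated, so DE = 2.0 and effective n = 150. For 80% power, CAMI per-visit positivity must fall from an assumed 10% to 2.3%, 20% to 8.7%, or 30% to 16.4% (relative cuts of 77%, 56.5% and 45%). At an assumed 5%, no reduction reaches 80%. For the 97% claim, with the same effective n, an assumed 30% must fall to 12.1%, or 50% to 28.6%.

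Incident STI also requires a negative baseline test. If the planning rates were per girl at risk and a share f is negative at baseline, a nominal 80% becomes Φ(2.80·√f − 1.96): 76% at f = 0.9 and 71% at f = 0.8 (both assumed). These results show what the claims would require; they neither confirm nor refute them.

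**The case for a change.** The best argument for a change is that the plan says power analysis determined the sample size, yet the analysis as printed cannot be rerun. The omissions are not redactions. The consequences are not small: on a normal approximation, Aim 1 moves from 94% to 77% as the assumed DEC rate goes from 4% to 7%. Anyone reading a null result on initiation or STIs would like to know the effect the trial was built to detect, and a few lines would supply it.

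Much of this stands. The Aim 1 control rate and the Aim 3 rates are missing, and 2.5 does not match three visits. But Aim 2's rates and Aim 3's three occasions are printed, and Aim 2's 80% has a plain approximate source. The less favourable Aim 2 and Aim 3 figures depend on rates that nobody has stated; for Aim 3, the required relative cut falls below half once the assumed DEC rate reaches 30%. The doubt over 200 or 250 girls in Aim 1 does no harm, because basing power on 200 is the cautious choice.

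**Conclusion.** This is a gap in reporting, not an error that calls for a change. Aim 1's 95% is plausible and Aim 2's 80% is approximately matched by a single-visit test. Aim 3's 80% and 97% are unverifiable rather than wrong. The 2.5 against 2.0 mismatch leaves power at 88% or 94% if 9% and 24% are final proportions. If they are increases, power could fall below 80%, but only at starting levels assumed from outside the documents.

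Supplying the inputs would not alter the target of 250, the outcomes, the models or the handling of missing data. The document is dated August 2023 and describes recruitment and follow-up in the past tense, so the planning figures no longer steer any decision. What the trial can exclude will be read from its estimates and confidence intervals (the Aim 1 analysis plans odds ratios with 95% intervals), not from planned power. The computed figures assume equal arms and 100 girls per arm unless shown otherwise. For repeated visits they also assume a constant correlation of 0.50 and a visit-averaged difference; they say nothing about power for treatment by time.

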Specific Aim #3, decrease in unsafe sexual activity, the primary outcome is incident STIs. The following is assumed: Type I error of $\alpha=.05$, an average within-subject correlation of 0.50 and 20% attrition rate. Using similar procedures as above, the proposed enrollment of 250 participants at baseline will achieve power of 80% to detect differences after considering 3 repeated measures (3, 6, 9 months). For the secondary outcome in Specific Aim #3, decrease in unsafe sexual activity, the following is assumed: Type I error of $\alpha=.05$, an average within-subject correlation of 0.50 and 20% attrition rate. Using the similar procedure as above, the proposed enrollment of 250 participants at baseline will achieve power of 97% to detect assumed differences. The proposed sample size may provide greater power to detect interaction effects, robustness to violations of model assumptions, protection against multiple comparison error rates, and increase efficiency to detect weaker relationships between variables.

Descriptive Analysis. Initially, descriptive statistics were used to summarize the variables as well as detect outliers, data entry mistakes, and missing values. Effectiveness of the randomization procedures was assessed through comparison of the two treatment arms on all baseline measures. Comparisons of baseline characteristics used Student's t-test, and Chi-square test. Data analyses were performed using "Statistical Analysis Software" (SAS Institute, Inc, Cary, North Carolina). All significance tests will be two-tailed.

Primary Analyses. Following intention-to-treat principles, all participants who have been randomized to the two conditions will be included in the analyses. Differential attrition across treatment groups was not expected, but this unlikely occurrence was assessed.

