Contraceptive Initiation (Aim #1). Analyses of contraceptive initiation included the percentage starting a highly effective method (DepoProvera or an IUD) and highly effective methods requiring regular non-coital use (contraceptive pills, vaginal rings, the patch etc). This intent-to-treat analysis used multiple logistic regression to determine if girls randomized to the CAMI condition were more likely to initiate a contraceptive method than girls randomized to the DEC condition. The background characteristics (age, gender, race) or baseline characteristics (e.g., pregnancy related variables, and contraceptive history) and some meaningful interaction terms will be incorporated in the initial full model. All the p values are calculated with two-sided significance level of 0.05. Odds ratios and their 95% confidence intervals will be calculated for any important explanatory variables.

Contraceptive Continuation (Aim #2). Testing interactions between treatment and time illuminated whether differences in contraceptive outcomes between treatment conditions became more or less pronounced over the 9 months of follow-up.

Incident STIs (Aim #3). All STIs tested through the study were evaluated. Generalized linear mixed model (GLMM) were used to test this hypothesis, and procedures similar to those outlined in Aim #2 were used.

Secondary Analyses (Aim #2 and Aim #3). The following were utilized 1) pregnancy incidents and 2) the TLFB to identify the percentage of at-risk-days that girls engage in unprotected sexual activity. GLMM was used to test this hypothesis, and procedures similar to those outlined in Aim #2 will be followed.

Predictors of contraceptive use. These included demographics of age, race/ethnicity and education as well as drug and alcohol use, recent and childhood victimization and pregnancy history. Measurement modeling was used to incorporate multiple measures, such as the self-reported primary outcomes and the incidence of pregnancy and STD in a latent factor that captures variance common to all measures²⁴.

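### As powered, Aim 2 compares use of a highly effective method among all randomized girls, so a positive result cannot separate better continuation from more initiation (Aim 1)

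*Combined protocol and SAP*

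**What the plan says.** Under Study Objectives, the Aim 2 hypothesis compares the randomized groups: girls assigned to CAMI "will be more likely to continue the use of highly effective contraception" at 3, 6 and 9 months than girls assigned to DEC. Under Primary Analyses, "all participants who have been randomized to the two conditions will be included in the analyses".

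The Aim 2 paragraph of Sample Size Considerations states that "approximately 125 subjects for each group at baseline will provide 80% power for this analysis", allows for attrition, and gives the effect in a parenthesis: "assume continuation increase of 9% for controls and 24% for the intervention group, based on CAMI pilot data". The Aim 1 paragraph just before it expects a moderate effect, "resulting in 20% starting a contraceptive method in the treatment group", and gives no DEC rate.

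Three further places bear on the point:
- **Primary Outcomes.** The only scoring rule for continuous use concerns switching between methods.
- **Contraceptive Continuation (Aim #2).** This analysis paragraph describes only a treatment-by-time interaction.
- **Selection, and the account of CAMI Session 2.** Girls already using a method at entry are not excluded, and the session content provides for girls whose behavior is already safe.

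No section says how a girl who never starts is scored under Aim 2, restricts Aim 2 to starters or baseline users, or separates staying on a method from starting one.

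**The concern.** A girl can continue a method only once she is using it. If every randomized girl is in the denominator, one who never starts cannot count as a success. The Aim 2 proportion is then the share who are ever on a method multiplied by the share of those who persist. Any difference in initiation passes straight into it.

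Aims 1 and 2 each have their own primary outcome, so two positive results would be read as two effects: CAMI helps girls start, and CAMI helps them stay on. The second could follow from the first with no effect on persistence.

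The obvious alternative, dropping girls who never start, does not repair this. It conflicts with the intention-to-treat statement, and it compares groups formed after randomization by something the intervention is meant to change.

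**Working it through.** **Step 1. Which girls does the 80% power count?**

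Inputs from the plan are 9% v 24%; 125 per arm at baseline; "power after considering 20% attrition rate over 9 months", which gives 125 × 0.8 = 100 per arm; and two-sided 0.05 ("All the p values are calculated with two-sided significance level of 0.05", stated in the Aim 1 analysis paragraph).

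With p̄ = (p₁ + p₂)/2, the pooled normal approximation is

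power = Φ{[|p₂ − p₁|√n − 1.96√(2p̄(1 − p̄))] / √(p₁(1 − p₁) + p₂(1 − p₂))}, plus the negligible opposite tail.

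- One visit, n = 100: 82.0%. Fisher's exact test gives 78.5%. Both are close to the stated 80%.
- The plan also cites a design effect: "Assuming an average within-subject correlation of 0.50, corresponding to a design effect of 2.5". The usual form 1 + (m − 1) × 0.50 gives 2.5 for m = 4 and 2.0 for the m = 3 follow-ups. Three visits with 2.5 give an effective n of 300/2.5 = 120 and power of 88.4%. With 2.0, n = 150 and power is 94.2%. Dividing 100 by 2.5 with no credit for repeats gives n = 40 and 43.8%. None of these is 80%.
- If 9% and 24% were rates among starters only, power would be about 5% with 4 v 20 starters, 6% with 5 v 20, and 19% with 15 v 40.

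Of the readings tried, the stated power fits only a single-visit comparison of all retained girls.

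**Step 2. What DEC start rate does Aim 1 imply?**

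The rate is not given. If 20% is the CAMI rate, the same formula at 100 per arm gives 95.0% power for a DEC rate of 3.75%, 94.2% for 4%, 90.0% for 5% and 50.8% for 10%. About 4% therefore matches the stated 95%. I use 4% to 10% as an assumed range.

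**Step 3. Carry-over when the effect on persistence is zero.**

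Let b be the share already using a method at baseline, s the start rate among non-users, and r the persistence, the same in both arms and for both kinds of user. Then

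Aim 2 proportion = [b + (1 − b)s] × r.

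Example with b = 0 and r = 0.75: CAMI 0.20 × 0.75 = 15%, DEC 0.04 × 0.75 = 3%. At 100 per arm this is significant in 85% of trials.

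Example with b = 0.10, r = 0.90 and DEC s = 0.04: CAMI (0.10 + 0.90 × 0.20) × 0.90 = 25.2%, DEC (0.10 + 0.90 × 0.04) × 0.90 = 12.2%. This is significant in 65%.

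Chance of a significant result, CAMI s = 20%, both tails counted:

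| Baseline users | DEC start | r = 60% | r = 75% | r = 90% |
|---|---|---|---|---|
| 0% | 4% | 75% | 85% | 91% |
| 0% | 10% | 32% | 39% | 46% |
| 10% | 4% | 46% | 56% | 65% |
| 10% | 10% | 19% | 24% | 29% |
| 20% | 4% | 29% | 37% | 45% |
| 20% | 10% | 14% | 17% | 20% |
| 30% | 4% | 20% | 26% | 32% |
| 30% | 10% | 11% | 13% | 15% |

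If b is instead chosen so that DEC equals the plan's 9% with a 4% start rate, then b = (0.09/r − 0.04)/0.96, which is 11.5%, 8.3% and 6.3% for the three values of r. The chances are 43%, 60% and 75%.

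**Step 4. Is initiation the cause?**

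In a three-visit simulation (20,000 runs, 100 per arm, 80% of users retained per interval, no baseline users), Aim 2 was significant in 89% of runs with 5% v 20% starting and 47% with 10% v 20%. With equal initiation (20% v 20%) the figure fell to 5.1%.

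**Step 5. The treatment-by-time interaction.**

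With 5% v 20% starting and 80% retained per interval, the proportions are 5% v 20%, 4% v 16% and 3.2% v 12.8%. The log odds ratios are 1.56, 1.52 and 1.49. The arm difference is nearly constant over time, so the interaction stays near null although the arms differ clearly at each visit.

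**The case against.** The strongest reply is that the only Aim 2 test actually described is the treatment-by-time interaction, which by Step 5 need not inherit the Aim 1 effect. That is correct, and it limits the point to the between-arm contrast. It does not remove it: the hypothesis and the 9% v 24% are about that contrast, and an interaction asks whether the arm difference changes over time, not by itself whether CAMI girls continue more.

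Four stronger readings are tempting, and the documents do not support them.
- **That the plan scores a never-starter as not continuing, or a girl who starts in month 8 as continuing at month 9.** Neither rule is written. The first is an inference from including everyone in an outcome of continued use. The second has no textual basis, and the outcome's label of continuous use points the other way.
- **That 20% starting and a 24% increase in continuation contradict each other.** They would only if both were percentage points of all CAMI girls over the same period. The increase may be relative, the 20% may refer to non-users, and baseline users could supply the difference of 4 points. What is missing is a stated denominator.
- **That 85% is the size of the problem.** It needs no baseline users and a DEC start rate near 4%, and it puts DEC at 3% where the plan assumes 9%. Baseline users dilute the carry-over considerably.
- **That the comparison is invalid.** Use among all randomized girls is a sound randomized comparison. The fault lies in calling it continuation.

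**Conclusion.** The concern stands in a limited form. The plan does not define the Aim 2 denominator or the scoring of girls who never start. On the natural reading, which the stated power supports, the powered contrast mixes initiation with persistence, and a positive result cannot be separated from an Aim 1 effect.

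With no true effect on persistence, the chance of a significant Aim 2 result is about 32% to 91% without baseline users and about 11% to 65% with 10% to 30% baseline users, against a nominal 5%. These figures assume 100 retained per arm, a single-visit two-proportion test, 20% of CAMI non-users starting, and equal persistence of 60% to 90%. The DEC start rate (4% to 10%), the baseline-user share and the persistence are my assumptions, since the documents give none of them. The direction of the conclusion does not depend on the values chosen; the size does.

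**What to change.** 1. Keep the all-randomized comparison, but name it use of a highly effective method at each visit. State that a positive result does not by itself show better continuation.
2. Add a supportive analysis of CAMI v DEC continuous use at each visit among girls on a highly effective method at baseline by TLFB. Their use predates the intervention, so the comparison stays randomized.
3. Report persistence among girls who start after baseline by arm, as description only.
4. State the denominator of the 20% and of the 9% and 24%, and whether the latter are levels, absolute rises or relative rises. As written, they cannot be compared.

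The cost is wording in the analysis plan and one subset analysis of data already collected. The Aim 2 claim becomes narrower. The baseline-user subset is probably small (its size is not given), so its estimate will be imprecise, and it does not cover girls who start because of CAMI.
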